4.3. Sample Size Determination

Due to the dynamic nature of the Bayesian allocation procedure, the sample size using the mTPI approach cannot be determined in advance in the dose escalation phase of the study. The target sample size for each cohort is 2 to 4, the actual number of patients treated at each dose will vary from 2 to 12. It is estimated that the maximum sample size will be approximately 72 patients in Part 1 of the study, although this may be higher if more than 6 dose levels are required to be evaluated. Up to approximately 20 to 25 patients are anticipated to be enrolled in Part 2 of the study.

In Part 2, the expansion phase of the study, multiple efficacy endpoints will be investigated, namely: 1) disease control rate (DCR) at Week 9; 2) DCR at Week 25; 3) objective response rate (ORR) by MRI by or at Week 9; 4) ORR by F-18-FLT-PET scan by or at Week 9 (if collected). The sample size is driven by DCR at Week 9 and ORR by MRI.

The expansion phase of the study will be a single arm study, the recommended dose from Part 1 will be used in this phase. With 20 patients, the study will have an approximately 75% power to detect a 25% improvement in Disease Control Rate (DCR), aiming for a 65% DCR, from the null hypothesis of 40% DCR. The study will have an approximately 78% power to detect a 15% improvement in ORR, aiming for a 20% ORR, from the null hypothesis of 5% ORR. These sample size calculations use a one-sample test for a single

proportion with a one-sided alpha level of 0.05. The statistical power will be slightly higher than stated above if this phase of the study enrolls more than 20-25 patients.

5. ANALYSIS SETS

5.1. Safety Analysis Set

The safety analysis set includes all enrolled patients who receive at least one dose of study treatment.

5.2. Full Analysis Set

The full analysis set includes all enrolled patients. All efficacy endpoints will be analysed with this population.

5.3. Per-Protocol Analysis Set

The per-protocol analysis set includes all enrolled patients who receive at least one dose of study treatment and who do not have major treatment deviations during the 28-day observation period. Patients with major treatment deviations in this cycle are not evaluable for the MTD assessment and will be replaced as needed to permit MTD estimation. Major treatment deviations include:

- Administration of less than 50% of the planned dose of PF-06840003, provided that it is not due to toxicity attributable to PF-06840003;
- Administration of more than 150% of the planned dose of PF-06840003.

5.4. PK analysis sets

The PK parameter analysis population is defined as all enrolled patients treated who have sufficient information to estimate at least 1 of the PK parameters of interest.

The PK concentration population is defined as all enrolled patients who are treated and have at least 1 analyte concentration.

5.5. Biomarker analysis set(s)

The biomarker analysis set includes all enrolled patients with at least one of the PD/biomarker parameters evaluated at pre- and/or post-dose.

5.6. Treatment Misallocations

For patients with errors in treatment allocation the following approach will be followed:

If a patient was:

• Enrolled but not treated, then they will be reported under their enrolled treatment group for demographic analyses only. These patients will be excluded from the immunogenicity, efficacy and safety analyses as the actual treatment is missing;

• Enrolled but took incorrect treatment, then they will be reported under their enrolled treatment group for efficacy analyses, excluded from analyses based on PP, but will be reported under the treatment they actually received for all safety, PK, immune responses, and immunogenicity analyses.

5.7. Protocol Deviations

Protocol deviations will be determined on an ongoing basis per medical data review. Any major protocol deviation will prevent the patient from being included in the per-protocol population.

A full list of major protocol deviations will be compiled prior to database closure. Once the final list of major protocol deviations is determined the per-protocol population flag will be updated.

6. ENDPOINTS AND COVARIATES

6.1. Primary Endpoint – Part 1

• Incidence and grade of treatment-emergent adverse events (TEAE) including Dose Limiting Toxicity (DLTs) as graded by National Cancer Institute Common Terminology Criteria for Adverse Events (CTCAE) version 4.03. The specific definition of DLT is provided in the study protocol.

6.2. Primary Endpoint – Part 2

- Adverse Events (AE) as characterized by type, frequency, severity, timing, seriousness, and relationship to study therapy.
- Disease control rate (DCR) at 9 and 25 weeks by MRI using Macdonald criteria (Macdonald et al, 1990). DCR is defined as the proportion of patients achieving CR, PR, or SD as assessed by MacDonald criteria.

6.3. Secondary Endpoint

- Laboratory abnormalities as characterized by type, frequency, severity (as graded by NCI CTCAE v.4.03) and timing;
- Vital Signs;
- PK parameters in the blood of PF-06840002 and PF-06840001 Single Dose (SD) C_{max}, T_{max}, AUC_{last}, AUC_τ, CL/F, and V_z/F and t_{1/2}, AUC_{inf} as data permit. Multiple Dose (MD) (assuming steady state is achieved) – C_{ss,max}, T_{ss,max}, AUC_{ss,τ}, t_{1/2}, C_{ss,min}, C_{ss,av}, CL/F, V_z/F, R_{ac} (AUC_{ss,τ}/AUC_{sd,τ}) and R_{ss} (AUC_{ss,τ}/AUC_{sd,inf}) as data permit;
- *Objective tumor response based on Macdonald criteria.* Objective tumor response is defined as the proportion of patients achieving CR or PR as assessed by Macdonald criteria.

- Disease Control Rate at 9 and 25 weeks by MRI based on Response Assessment for Neuro-Oncology (RANO) criteria.
- On-target activity of PF-06840003 by measurement of kynurenine, tryptophan and kyn/trp (ratio) levels in peripheral blood.
- Steady-state trough level ratio between CSF and plasma samples for PF-06840002 and PF-06840001.

Not applicable.

7. HANDLING OF MISSING VALUES

7.1. Missing Values For Safety, Immune Responses, Pharmacodynamics, Immunogenicity, CCI

All the safety, immune responses, pharmacokinetic, pharmacodynamics, immunogenicity analyses and summaries will be based on data as observed and no explicit imputation will be applied.

7.2. Immune Responses Lower Limit Of Quantitation

Titers below the assay detection limit will be assigned a value of one-half that limit

7.3. Pharmacokinetic Concentrations And Parameters

Drug concentrations below the limit of quantification

In all data presentations (except listings), drug concentrations below the limit of quantification (BLQ) will be set to zero. In the listings BLQ values will be reported as "<LLQ", where LLQ will be replaced with the value for the lower limit of quantification.

Deviations, missing concentrations and anomalous values

Subjects who experience events that may affect their PK (eg, incomplete dosing) may be excluded from the PK analysis.

In summary tables and plots of mean profiles of PK, statistics will be calculated having set concentrations to missing if 1 of the following cases is true:

- 1. A concentration has been collected as ND (ie, not done) or NS (ie, no sample);
- 2. A deviation in sampling time is of sufficient concern or a concentration has been flagged anomalous by the PK analyst.

Note that summary statistics will not be presented at a particular time point if more than 50% of the data are missing.

An anomalous concentration value is one that, after verification of bioanalytical validity, is grossly inconsistent with other concentration data from the same individual or from other subjects. For example, a BLQ concentration that is between quantifiable values from the same dose is considered as anomalous. Anomalous concentration values may be excluded from PK analysis at the discretion of the PK analyst.

Pharmacokinetic parameters

Actual PK sampling times will be used in the derivation of PK parameters. In the event that the actual sampling time is not available, the nominal time may be used if there is no evidence that the actual sampling time deviates substantially from the nominal time.

If a PK parameter cannot be derived from a subject's concentration data, the parameter will be coded as NC (ie, not calculated).

In summary tables, statistics will be calculated by setting NC values to missing; and statistics will not be presented for a particular treatment if more than 50% of the data are NC. For statistical analyses (ie, analysis of variance, if applicable), PK parameters coded as NC will also be set to missing.

If an individual subject has a known biased estimate of a PK parameter (due, for example, to an unexpected event such as vomiting before all the drug is absorbed in the body), this will be footnoted in summary tables and will not be included in the calculation of summary statistics or statistical analyses.

8. STATISTICAL METHODOLOGY AND STATISTICAL ANALYSES

In general, all continuous endpoints will be summarized descriptively by dose level. If data are categorical then the standard contingency tables with counts and percent by dose level will be displayed.

8.2. Statistical Analyses

There are 2 parts in the study. Generally analysis output is to be generated for Part 1 and Part 2 separately, unless where it specifies a combined analysis is to be conducted.

8.2.1. Subject Disposition

Subject disposition will be summarized by dose level and will include the number of patients enrolled, treated, treated and completed the study, treated but did not complete the study and reason for early discontinuation from the study. Subject disposition summary will be generated using the full analysis set.

8.2.2. Subject Demographics and Baseline Characteristics

Demographic, ECOG performance status (Karnofsky Performance Score, as detailed in Appendix 2 of the study protocol), childbearing potential and other baseline characteristics CCI and number

of prior therapies) will be summarized by dose level using the full analysis set.

8.2.3. Study Treatment Exposure and Dose Intensity

Duration of treatment (number of days and number of cycles) will be summarized by dose level. Relative Dose Intensity (ratio of actually administered dose to scheduled/planned dose per unit time) will be summarized for each dose level and by cycle. Relative Dose will be summarized for each dose level across all cycles. Detailed algorithms for these calculations are provided in the appendix. (Appendix 1.1).

The number of patients with missed dose may be summarized by dose level.

Patient level study treatment administration data will be listed in chronological order by dose level.

These analyses will be performed with the safety analysis set.

8.2.4. Safety Analysis

Safety analysis will be based on the safety analysis set.

8.2.4.1. Analysis of Primary Safety Endpoint

In Part 1 of the study, dose limiting toxicity (DLT) is a primary endpoint. Adverse events constituting DLTs are detailed in the study protocol. Adverse events constituting DLTs will be listed by dose level. A binary variable will be created at the patient level to indicate whether or not a patient has experienced any of the adverse events that are considered DLT. If required, a summary table will be created by dose to present number and percentage of patients experiencing DLT.

Treatment-emergent adverse events (TEAE) are defined as those events that occur after the first dosing or any pre-existing adverse event that worsened after the first dosing. The lag time required for defining TEAE will be based on Pfizer Standard. TEAE will be listed by dose level where system organ class and preferred term as well as other collected variables about the AE will be displayed. If necessary, a summary table for TEAE by system organ class and preferred term for each dose level will be generated. Similarly serious adverse events (SAE), and treatment related SAEs will be listed. Summary tables may be generated if necessary.

In Part 2, TEAE, treatment related TEAE, SAE, and treatment related SAEs will be listed and summarized. TEAE will also be summarized by CTC AE (version 4.03) grade and by system organ class and preferred term.

8.2.4.2. Analysis of Secondary Safety Endpoint

These safety endpoints will be analyzed according to the Pfizer Data Standard.

Laboratory Tests Abnormalities

Laboratory tests will be listed by dose level and cycle and day. Upon reviewing the lab data listing, if study team deems necessary, summary tables and tables presenting the change and percent change from baseline may be generated by dose level and cycle and day. Shift tables may be provided to examine the distribution of laboratory toxicities. Shift tables will be created for each laboratory test for baseline relative to each post-baseline measurement by maximum CTCAE grade, cycle, and dose. The most recent measurement prior to dosing is considered as baseline.

On-target activity of PF-06840003 by measurement of kynurenine, tryptophan and kyn/trp (ratio) levels in peripheral blood will be listed by dose and cycle and day.

Vitals signs

Vital signs, (ie, body temperature and blood pressure), will be listed by dose level and cycle and day. Upon reviewing the vital signs data listing, if study team deems necessary, summary tables and tables presenting change and percent change from baseline may be generated by dose level and cycle and day. The most recent measurement prior to dosing is considered as baseline.

ECG

The analysis of ECG results will be based on patients in the safety analysis set with baseline and on-treatment ECG data. Baseline is defined as the latest assessment prior to receipt of the first dose (ie, Cycle 1 Day 1), ie, the average of the latest pre-dose triplicate ECG on Cycle 1 Day 1. If the Cycle 1 Day 1 timepoint is not available, the screening assessment will be used as the baseline.

ECG measurements (an average of the triplicate measurements) will be used for the statistical analysis and all data presentations. Any data obtained from ECGs repeated for safety reasons after the nominal time-points will not be averaged along with the preceding triplicates. Interval measurements from repeated ECGs will be included in the outlier analysis (categorical analysis) as individual values obtained at unscheduled time points.

QT intervals will be corrected for heart rate (QTc) using standard correction factors (ie, Fridericia's). Data will be summarized and listed for QT, HR, response rate (RR), PR, QRS, QTcF, and dose. Individual QT (all evaluated corrections) intervals will be listed by time and dose. The most appropriate correction factor will be selected and used for the following analyses of central tendency and outliers and used for the study conclusions. Descriptive statistics (n, mean, median, standard deviation, minimum, and maximum) will be used to summarize the absolute corrected QT interval and changes from baseline in corrected QT after treatment by dose and time point. For each patient and by treatment, the maximum change from baseline will be calculated as well as the maximum post-baseline interval across time-points. Categorical analysis will be conducted for the maximum change from baseline in corrected QT and the maximum post-baseline QT interval.

Shift tables will be provided for baseline vs worst on treatment corrected QT using maximum CTCAE Grade. Patients experiencing clinically-relevant morphological ECG changes will be summarized (including frequency and percentage).

The effect of drug concentrations on corrected QT change from baseline will be explored graphically. Additional concentration-corrected QT analyses may be performed. Data may be pooled with other study results and/or explored further with PK/PD models.

Physical Examination

Physical examination results will be listed by dose level and cycle. Upon reviewing the subject level data listing, if study team deems necessary, summary table may be generated by dose level and cycle.

ECHO/MUGA

LVEF (left ventricle ejection fraction) results from the cardiac function evaluation by ECHO or MUGA will be listed by dose level and cycle in a subject data listing. Upon reviewing the subject data listing, if study team deems necessary, summary table of LVEF over time and/or change from baseline in LVEF may be generated by dose level and cycle.

8.2.5. Efficacy Analysis

Efficacy will be investigated in both Part 1 and Part 2 of the study.

8.2.5.1. Primary Efficacy Analysis

Tumor assessments including MRI will be performed every 8 weeks (with an allowable window per study protocol) after the first dose. Disease control rate (DCR), defined as the proportion of patients achieving CR, PR, or SD as assessed by Macdonald criteria, will be summarized and listed by dose level and week. A cycle is 4 weeks long. Number of weeks will be derived based on cycle numbers. This will be performed for Part 1 and Part 2 separately. If deemed necessary and data permits, a combined analysis may be performed where Part 2 and the same dose level in Part 1 as that in Part 2 will be combined. These analyses will be based on investigator provided overall disease assessment.

As data accumulates, a Bayesian approach with a non-informative Jeffery's prior beta (0.5, 0.5) will be used to calculate the posterior probability of observing certain DCR (eg, 40%, 50%, 60% etc.). The purpose of it is to monitor data on an ongoing basis and to provide more analytical data for the study team. No official analysis output needs to be generated for this. This is only applicable to Part 2.

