| CCI ██████████                                       | █   |   |       |               |                |                | █                            |                | █  |                | █                   |                             |
| CCI ██████████                                       | █   |   |       |               |                |                |                              |                | ██████████                                   |                | █                   |                             |
| Adverse events                          |   | X   | X     | X             | X              | X              | X                            | X              | X  | X              | X                   | X                           |
| CCI ██████████                                       | █   | █   | █     | █             | █              | █              | █                            | █              | █  | █              | █                   | █                           |
| Other samplings                               |   |   |       |               |                |                |                              |                |  |                |                     |                             |
| Banked biospecimen                                   |   | X   |       |               |                |                |                              |                |  |                |                     |                             |
| Tumor biopsy   |   | Refer to Schedule of Electrocardiogram, Pharmacokinetic and Pharmacodynamic Assessments |       |               |                |                |                              |                |  |                |                     |                             |
| Pharmacokinetics                                     |   |   |       |               |                |                |                              |                |  |                |                     |                             |
| Pharmacodynamics                                     |   |   |       |               |                |                |                              |                |  |                |                     |                             |

\* A cycle is 28 days in duration

\*\* Visit windows are calculated off the first day of each cycle.

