14. **Tumor Assessments:** Tumor assessments will include all known or suspected disease sites. Imaging should include brain MRI with contrast. Tumor assessments will be made using the Macdonald criteria. On study MRIs are to be collected every 8 weeks ( $\pm 5$  days). Where possible, responses should be confirmed with two assessments at least 4 weeks apart. Tumor assessment should be repeated at the end of treatment visit if more than 4 weeks have passed since the last evaluation. Efficacy evaluations using the Macdonald criteria involve post-contrast MRI findings, non-contrast T1 and T2 fluid attenuated inversion recovery (FLAIR) images, use of corticosteroid dose, and neurological examination. Disease progression will be confirmed with two consecutive timepoints at least 8 weeks apart in the absence of substantial neurological decline if progression is suspected within 6 months of treatment initiation.
15. **F-18-fluorothymidine (FLT) PET:** For locations who are able to perform the assessment, 1 F-18-FLT-PET imaging will be performed in all patients assigned to receive doses of 500 mg/day or higher. Assessment will be performed at screening after all eligibility criteria have been confirmed and at Weeks 9 and 25. Should be performed if the patient discontinues the study prior to Week 9 or between Weeks 9 and Week 25 if more than 4 weeks have passed since the last evaluation.

CCI  
[Redacted text block]

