##### **5.4.1. Recommended Dose Modifications**

Every effort should be made to administer investigational product on the planned dose and schedule.

In the event of significant toxicity, dosing may be delayed and/or reduced as described below. In the event of multiple toxicities, dose modification should be based on the worst toxicity observed. Patients are to be instructed to notify investigators at the first occurrence of any adverse symptom.

Dose modifications may occur in one of three ways:

- Within a cycle: dosing interruption until adequate recovery and dose reduction, if required, during a given treatment cycle;
- Between cycles: next cycle administration may be delayed due to persisting toxicity when a new cycle is due to start;
- In the next cycle: dose reduction may be required in the current and/or subsequent cycle based on toxicity experienced in the current/previous cycle.

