#### **5.4.2. Dosing Interruptions**

Patients experiencing the following adverse events should have their treatment interrupted:

- Grade 3 or 4 potentially treatment related toxicity;
- Intolerable Grade 2 toxicity despite supportive care.

Appropriate follow up assessments should be done until adequate recovery occurs as assessed by the investigator. Criteria required before treatment can resume are described in [Section 5.4.3 Dose Delays](#).

Doses may be held as needed until toxicity resolution. Depending on when the AE resolved, a treatment interruption may lead to the patient missing all subsequent planned doses within that same cycle or even to delay the initiation of the subsequent cycle.

If the AE that led to the treatment interruption recovers within the same cycle, then re-dosing in that cycle is allowed. Doses omitted for toxicity are not replaced within the same cycle. The need for a dose reduction at the time of treatment resumption should be based on the criteria defined in section [Dose Reductions](#), unless expressly agreed otherwise following discussion between the investigator and the sponsor.

In the event of a treatment interruption for reasons other than treatment-related toxicity (eg, elective surgery) lasting >4 weeks, treatment resumption will be decided in consultation with the sponsor.

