#### **5.4.3. Dose Delays**

Re-treatment following treatment interruption for treatment-related toxicity or at the start of any new cycle may not occur until all of the following parameters have been met:

- ANC  $\geq 1,000/\text{mm}^3$ .
- Platelet count  $\geq 50,000/\text{mm}^3$ .
- Non-hematologic toxicities have returned to baseline or Grade  $\leq 1$  severity (or, at the investigator discretion, Grade  $\leq 2$  if not considered a safety risk for the patient).

If a treatment delay results from worsening of hematologic or biochemical parameters, the frequency of relevant blood tests should be increased as clinically indicated.

If these conditions are met within 2 weeks of treatment interruption or cycle delay, PF-06840003 dosing may be resumed. Refer to Section Dose Reductions for AEs requiring dose reduction at the time of treatment resumption.

If these conditions are not met, treatment resumption must be delayed up to a maximum of 2 weeks. If these parameters have not been met after 2 weeks of dosing interruption, or 2 weeks of new cycle delay, permanent discontinuation of treatment with PF-06840003 should be considered. Treatment resumption for patients recovering from treatment-related toxicity after >2 weeks of treatment interruption or cycle delay may be considered only if the patient is deemed to be deriving obvious clinical benefit per the investigator's best medical judgment and needs to be agreed between the investigator and the sponsor.

If a treatment interruption continues beyond Day 28 of the current cycle, then the day when treatment is restarted will be counted as Day 1 of the next cycle.

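### The SAP takes the week of the Part 2 primary DCR from cycle number, but cycle starts can slip while MRIs are counted from first dose, so Week 9 and Week 25 can be mislabelled

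*SAP*

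**What the plan says.** SAP 6.2 and Protocol 2.2 define the Part 2 primary efficacy endpoint as DCR by MRI at 9 and 25 weeks under the Macdonald criteria.

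SAP 8.2.5.1 uses two clocks in one paragraph. The scan schedule runs from first dose: "Tumor assessments including MRI will be performed every 8 weeks (with an allowable window per study protocol) after the first dose". The week used in the summary does not: a cycle is taken as 4 weeks, and "Number of weeks will be derived based on cycle numbers".

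The protocol sets the imaging interval in footnote 14 of the Schedule of Activities: "On study MRIs are to be collected every 8 weeks", within ±5 days. Section 7.4 repeats this. Neither place says that scans move when a cycle is delayed. A separate note to the Schedule says "Visit windows are calculated off the first day of each cycle".

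Cycles need not last 28 days:

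- Protocol 5.4.1: "next cycle administration may be delayed due to persisting toxicity when a new cycle is due to start".
- Protocol 5.4.3, for toxicity: "treatment resumption must be delayed up to a maximum of 2 weeks". A longer delay is possible by agreement between investigator and sponsor.
- Protocol 5.4.3, if an interruption runs past Day 28: "then the day when treatment is restarted will be counted as Day 1 of the next cycle".
- Protocol 5.4.2 asks for sponsor consultation on resuming after a "treatment interruption for reasons other than treatment-related toxicity (eg, elective surgery) lasting >4 weeks".

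SAP 5.2 analyses all efficacy endpoints in the full analysis set.

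**The concern.** Cycle number converts to weeks from first dose only while every cycle lasts exactly 28 days. The protocol expressly allows otherwise. The SAP also recognises this elsewhere: its Appendix 1.1 computes dose intensity from actual cycle start dates.

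Once a cycle has slipped, two things can go wrong. A scan taken on time can carry an earlier week and drop out of the Week 9 or Week 25 summary. Or a scan postponed with the cycle can be reported as on time. Neither document, as far as it is visible, gives a date window that assigns a scan to Week 9 or Week 25.

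At stake is the reproducibility of the primary Part 2 efficacy estimate: two programmers could obtain different DCRs from the same scans. The same by-week summary is used in SAP 8.2.5.2 for ORR and for DCR under RANO.

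**Working it through.** **Inputs.** First dose is Day 1. Nominal cycle length is 28 days (SAP 8.2.5.1). The MRI window is ±5 days (Schedule of Activities, footnote 14; Protocol 7.4). The standard limit on a toxicity delay is 14 days (Protocol 5.4.3). Part 2 has 20 patients in the sample-size calculation (SAP 4.3).

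**Formulas.** With accumulated delay *d* in days before cycle *c*:

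- Cycle *c* Day 1 = 28(*c* − 1) + 1 + *d*
- Calendar week of a day = floor((day − 1)/7) + 1
- Week implied by the cycle number = 4(*c* − 1) + 1

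**No delay (the plan's own labels).** Cycle 3 Day 1 = 28×2 + 1 = Day 57, and floor(56/7) + 1 = Week 9. Cycle 7 Day 1 = 28×6 + 1 = Day 169, and floor(168/7) + 1 = Week 25. The cycle rule gives 4×2 + 1 = 9 and 4×6 + 1 = 25. The clocks agree, and the windows are Days 52–62 and 164–174.

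**One 14-day delay before Cycle 3.**

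| | Nominal day | Day after delay | Calendar week | Label from cycle number |
|---|---|---|---|---|
| Cycle 3 Day 1 | 57 | 57 + 14 = 71 | floor(70/7) + 1 = 11 | 9 |
| Cycle 7 Day 1 | 169 | 169 + 14 = 183 | floor(182/7) + 1 = 27 | 25 |

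*Scan kept on the first-dose clock.* A Day 57 scan precedes Cycle 3 Day 1 (Day 71), so it lies in Cycle 2, which implies Week 4×1 + 1 = 5. A Day 169 scan lies in Cycle 6, which implies Week 4×5 + 1 = 21. This assumes that a cycle runs until the next one starts, as in SAP Appendix 1.1, and that the scan takes the number of the cycle in progress on its date.

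*Scan moved with the cycle.* Days 71 and 183 are each 9 days past the end of the window (71 − 62 and 183 − 174), yet they are labelled Week 9 and Week 25. A scan on cycle Day 1 leaves the window from *d* = 6, since 57 + 6 = 63 > 62 and 169 + 6 = 175 > 174.

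*Scan recorded to a nominal visit.* An on-time scan keeps the right label.

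**Effect of one patient.** The full analysis set keeps the patient in the denominator. If the patient was controlled but the scan loses its label, DCR falls by 1/20 = 5.0 points. At the plan's target rate, 13/20 = 65% becomes 12/20 = 60%; at its null rate, 8/20 = 40% becomes 7/20 = 35%.

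**The case against.** The strongest reply is that the sentence is simply a nominal-visit conversion: Cycle 3 means Week 9 and Cycle 7 means Week 25. The Schedule of Activities shows the MRI in the column for Cycle 3 onward, so a scan taken a few days before Cycle 3 Day 1 would be the Cycle 3 assessment done early. If scans are recorded that way, on-time scans keep their labels. That stands as a possible practice, but no visible passage states it. It also does not stop a scan postponed with the cycle from being labelled on time. Such a scan would be a departure from the imaging schedule, but the week rule would not reveal it.

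Four stronger readings are tempting, and the documents do not support them:

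- *Many on-time scans are mislabelled even without any delay*, because Days 52–56 fall in Cycle 2 and Days 164–168 in Cycle 6. This needs scan dates to be sorted into cycles by calendar, which the SAP does not direct.
- *A patient without a labelled scan might leave the denominator, so even the sign of the error is unknown.* SAP 5.2 puts all efficacy endpoints on the full analysis set, and SAP 5.6 excludes from efficacy only patients enrolled but not treated. On the plain reading, a treated patient stays in.
- *Death and deterioration are not covered.* Protocol 7.4 already counts failure to return for either reason as progression.
- *The trial loses power.* Protocol 9.4 makes DCR descriptive and SAP 4.1 states no hypotheses. The planned power of about 75% is not in question here.

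**Conclusion.** The concern holds as a definition defect in the Part 2 primary efficacy endpoint. The SAP gives an express rule, and that rule stops measuring weeks from first dose once a cycle start has slipped, which the protocol permits. A single delay at the standard 2-week toxicity limit moves the cycle-based Week 9 and Week 25 to calendar Weeks 11 and 27.

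The total effect cannot be sized, because the documents give no delay rate and do not say how scans are tied to visits. Per patient, a controlled patient whose scan loses its label lowers DCR by 5.0 points at n=20. That figure assumes labelling by the cycle in progress and a full-analysis-set denominator. For a late scan labelled on time, the claim is only that it could change that patient's classification.

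**What to change.** Replace the sentence on deriving weeks in SAP 8.2.5.1 with text to this effect:

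> Week is derived from MRI date relative to first-dose date, regardless of cycle number: Week 9 = Day 57 ±5 (Days 52–62), Week 25 = Day 169 ±5 (Days 164–174). The denominator is the full analysis set, subject to SAP 5.6. A patient with no CR, PR or SD scan in the window is counted as not controlled, and the number with no in-window scan is reported. A sensitivity analysis counts as controlled a patient with no in-window scan whose next later scan shows CR, PR or SD without earlier progression.

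Use the same week derivation for ORR and for DCR under RANO in SAP 8.2.5.2.

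The cost is a few lines of SAP text and one extra sensitivity table. It uses dates already collected and changes no visit, scan or dosing rule.
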